
Criteria for Evaluation: Safety
	
The primary safety endpoint is:
 
 1. Proportion of subjects with at least 1 AE comparing individual PTG-100 dosing groups with placebo 
The secondary safety endpoints (all based on comparison of individual PTG-100 dose levels to placebo) are:
 
 1. Frequency and type of AEs (affecting $\geq 5\%$ of subjects) 2. Proportion of subjects with at least 1 serious AE (SAE) 3. Number and type of SAEs 4. Frequency of AEs of special interest including serious or opportunistic infection (viral, bacterial, fungal including systemic/gut localization), allergic/drug reactions, immune system disorders, and suspected PML. 5. Clinically significant changes in safety labs, ECGs, or physical examination findings (including vital signs)

Criteria for Evaluation: PK, PD, and ADA
	
The PK/PD/ADA endpoints are:
 
 1. PTG-100 plasma levels 2. Blood $\alpha\beta 7$ RO (peripheral blood T cells) 3. Blood $\alpha\beta 7$ RE (peripheral blood T cells) 4. Proportion of subjects developing ADA by Weeks 12 (Day 84) and 16 (Day 112) 
The exploratory PD endpoints are:
 
 1. Analysis of peripheral blood lymphocytes in subjects on individual PTG-100 dose levels compared to placebo 2. Number of $\beta 7$ positive cells in colonic biopsies as assessed by immunohistochemistry in subjects on individual PTG-100 dose levels compared to placebo 3. Characterisation of immunologic biomarkers in the target population (selected sites only)

Statistical Methods:
	
Treatment population definitions:

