6.8 Final Treatment Day Clinical Site Visit (Day 84 or Early Termination)

The following assessments should be performed:

- AEs
- concomitant medications
- weight
- vital signs
- 12-lead ECG
- complete physical examination
- clinical laboratory evaluations (including haematology, coagulation, serum chemistry [fasting], CRP, and UA; see [Appendix B](#))
- PML subjective checklist (see [Appendix D](#)); any positive responses to the PML subjective checklist will require that the PML objective checklist be performed by the Investigator according to [Appendix D](#) and the study manual
- serum pregnancy test (WOCBP)
- sigmoidoscopy and biopsy
- complete Mayo Score assessment (rectal bleeding, stool frequency, PGA, and endoscopy subscores; see [Appendix A](#))
- IBDQ (see [Appendix G](#))

- faecal calprotectin
- PK blood sample (within 1 hour prior to dosing and 1, 2, and 4 hours \pm 20 minutes postdose)
- PD blood sample (within 1 hour prior to dosing and 4 hours \pm 20 minutes postdose; at selected sites only)
- ADA testing

Subjects who experience a flare of UC requiring rescue treatment that is prohibited in the protocol (in the judgement of the Investigator) will be discontinued from further treatment with study drug. Subjects who terminate early from treatment may be placed on appropriate therapy by the treating physician. Subjects will complete an Early Termination visit (including endoscopy) within 10 days following discontinuation, undergo the study procedures detailed in the Study Flow Chart ([Table 6-1](#)), and will be encouraged to be followed for all safety assessments through 28 days.

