7.5 Statistical Analysis of Safety Data

The primary safety endpoint is the proportion of subjects with at least 1 AE comparing individual PTG-100 dosing groups with placebo.

The secondary endpoints (all based on comparison of individual PTG-100 dose levels to placebo) will include:

1. Frequency and type of AEs (affecting $\geq 5\%$ of subjects)
2. Proportion of subjects with at least 1 SAE
3. Number and type of SAEs
4. Frequency of AEs of special interest including serious or opportunistic infection (viral, bacterial, fungal including systemic/gut localization), allergic/drug reactions, immune system disorders, and suspected PML
5. Clinically significant changes in safety labs, ECGs, or physical examination findings (including vital signs).

Continuous safety data will be summarised with descriptive statistics (arithmetic mean, standard deviation [SD], median, minimum, and maximum) by dose level. Categorical safety data will be summarised with frequency counts and percentages by dose level. Adverse events will be coded using the most current Medical Dictionary for Regulatory Activities available, which will be indicated in the Data Management Plan. A by-participant AE data listing, including verbatim term, preferred term, system organ class, treatment, severity, and relationship to study drug, will be provided. The number of participants experiencing treatment-emergent AEs (TEAEs) and number of individual TEAEs will be summarised by treatment group, system organ class, and preferred term. The TEAEs will also be summarised by severity and by relationship to study drug.

Laboratory evaluations, vital signs assessments, and ECG parameters will be summarised by treatment group and protocol-specified collection time point. A summary of change-

from-baseline at each protocol-specified time point by treatment group will also be presented.

Clinically significant changes in physical examinations will be listed for each participant and described in the text of the Clinical Study Report.

Medical history will be listed by subject.

Concomitant medications will be listed by participant and coded using the most current World Health Organization drug dictionary.

Further details regarding presentation and analysis of safety data will be detailed in the SAP.

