APPENDIX F - ADVERSE EVENTS

ADVERSE EVENTS

Definition of Adverse Events

An adverse event (AE; or adverse experience) is defined as any untoward medical occurrence experienced by a patient or healthy subject, whether or not considered drug related by the Investigator (or designee). A treatment-emergent AE is an AE that is reported after a dose of study drug.

The following are all AEs:

- unfavourable changes in general condition;
- subjective or objective signs/symptoms;
- concomitant diseases or accidents;
- clinically relevant adverse changes in laboratory parameters observed in a subject during a clinical study.

Adverse events comprise all disturbances of general health status, subjective and objective disease symptoms (including laboratory abnormalities), and accidents observed in the context of a clinical trial, irrespective of a possible causal relationship with the administration of the trial substance. Events occurring in the framework of a clinical trial during drug-free and post-treatment periods, under placebo, or in a reference group receiving drug or nondrug therapy are also to be designated as AEs.

Categorization of Adverse Events

The severity of AEs will be categorized as follows:

- **MILD** = of little concern to the subject and/or of no clinical significance, is not expected to affect the subject's health or well-being;
- **MODERATE** = discomforting enough to cause interference with or change in usual activities, is likely to require medical intervention or close follow-up;
- **SEVERE** = incapacitating or causing inability to work or participate in many or all usual activities, is of concern to the subject or poses substantial risk to the subject's health or well-being, is likely to require medical intervention or close follow-up.

The Investigator (or designee) will make a determination of the relationship of the AE to the study drug using a 4-category system according to the following guidelines:

- **NOT RELATED** = an AE that does not follow a reasonable temporal sequence from administration of the drug and can be reasonably explained by other factors, including underlying disease, complications, concomitant drugs, or concurrent treatment;

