### 4.2. General Statistical Methods and Data Handling

#### 4.2.1. General Methods

All output will be incorporated into Microsoft Excel or Word files, sorted and labeled according to The International Council for Harmonisation of Technical Requirements for Pharmaceuticals for Human Use (ICH) recommendations, and formatted to the appropriate page size(s).

Tabulations will be produced for appropriate demographic, baseline, efficacy, pharmacokinetic, pharmacodynamic and safety parameters. For categorical variables, summary tabulations of the number and percentage within each category (with a category for missing data) of the parameter will be presented. For continuous variables, the mean, median, standard deviation, minimum and maximum values will be presented.

Formal statistical hypothesis testing will be performed on the primary efficacy endpoint with all tests conducted at the 1-sided, 0.025 level of significance. Summary statistics will be presented, as well as confidence intervals on selected parameters, as described in the sections below.

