### 4.8.1. Adverse Events

The primary safety endpoint is the proportion of subjects with at least 1 AE comparing individual PTG-100 dose groups with placebo.

Secondary endpoints (all based on comparison of individual PTG-100 dose levels to placebo) will include:

- Frequency and type of AEs (affecting  $\geq 5\%$  of subjects)
- Proportion of subjects with at least 1 SAE
- Number and type of SAEs
- Frequency of adverse events of special interest (AESI) including serious or opportunistic infection (viral, bacterial, fungal including systemic/ gut localization), allergic/ drug reactions, immune system disorders, and PML or new onset neurologic symptoms

Adverse events will be coded using the Medical Dictionary for Regulatory Activities (MedDRA) and displayed in tables and listings using System Organ Class (SOC) and Preferred Term.

Analyses of adverse events will be performed for those events that are considered treatment emergent, where treatment emergent is defined as any adverse event with onset after the administration of study medication through the end of the study visit or any event that was present at baseline but worsened in intensity or was subsequently considered drug-related by the investigator through the end of the study.

Adverse events are summarized by subject incidence rates, therefore, in any tabulation, a subject contributes only once to the count for a given adverse event (SOC or preferred term).

The number and percentage of subjects

- with any treatment-emergent adverse event
- with any treatment-emergent adverse events assessed by the Investigator as related to treatment (definite, probable, or possible relationship)
- with any treatment-emergent serious adverse event
- with treatment-emergent adverse events by severity
- with adverse events affecting  $\geq 5\%$  of subjects within any treatment group across both stages of the study
- with AESI

will be summarized by treatment group and overall. In addition, all active groups will be pooled in the summaries for comparison to placebo. In these tabulations, each subject will contribute

only once (i.e., the most related occurrence or the most intense occurrence) to each of the incidence rates in the descriptive analysis, regardless of the number of episodes.

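### The any-AE primary safety endpoint does not exclude worsening of UC, which could flatter an effective dose; separately, no difference or confidence interval is planned for it

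*Protocol*

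**What the plan says.** Safety and tolerability is the first primary objective (Protocol 3). The synopsis gives the endpoint as "Proportion of subjects with at least 1 AE comparing individual PTG-100 dosing groups with placebo". Protocol 7.5 repeats it, and SAP 4.8.1 has: "The primary safety endpoint is the proportion of subjects with at least 1 AE comparing individual PTG-100 dose groups with placebo". The proportion with at least one SAE is a secondary safety endpoint.

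Three texts bear on whether a flare belongs in that count:

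- Protocol Appendix F: "Adverse events comprise all disturbances of general health status, subjective and objective disease symptoms (including laboratory abnormalities". The sentence goes on to accidents and applies whatever the cause.
- SAP 4.8.1 treats as treatment-emergent both new events after dosing and "any event that was present at baseline but worsened in intensity or was subsequently considered drug-related by the investigator".
- Protocol 6.8 foresees flares: "Subjects who experience a flare of UC requiring rescue treatment that is prohibited in the protocol" stop study drug and attend an Early Termination visit. It does not say whether the flare is entered as an AE.

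Protocol 6.13.2, Protocol 7.5, Appendix F and SAP 4.8.1 contain no exemption for the disease under study. The SAE definition in Appendix F contains none either.

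On analysis, Protocol 7.5 says "Categorical safety data will be summarised with frequency counts and percentages by dose level". In SAP 4.8.1 the numbers and percentages "will be summarized by treatment group and overall. In addition, all active groups will be pooled in the summaries for comparison to placebo". SAP 4.2.1 assigns formal testing to the primary efficacy endpoint and adds: "Summary statistics will be presented, as well as confidence intervals on selected parameters, as described in the sections below". Section 4.8 then describes no interval. By contrast, SAP 4.6.1 gives remission a 95% interval per arm and an odds ratio with its own interval.

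**The concern.** A flare in this population is mainly a sign that treatment has not worked. The sample-size section assumes about 10% remission on placebo and about 21 points more on drug. If anything like that holds, fewer flares on drug are plausible. Efficacy then enters the primary safety endpoint, in the drug's favour. A headline of no more AEs than placebo could reflect similar tolerability, or fewer flares set against more events of other kinds, and that row alone would not tell the two apart.

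A second, independent gap is that an endpoint worded as each dose against placebo has no planned measure of that contrast. The report would not state how large an excess the data leave open. Protocol 2.2 says this is the first use of the drug in UC, and dose selection at the interim analysis takes safety into account (Protocol 7.2).

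**Working it through.** **Is there a plan figure to reproduce?** The documents state no AE rate, flare rate or precision for safety. The only plan figure used here is the 70 to 80 subjects per selected arm in Protocol 7.2. With 60 Stage 1 subjects, about 60 overrun subjects and two doses kept at N = 240, it is (60 + 60)/4 + (240 − 120)/3 = 30 + 40 = 70. With 80 in Stage 1 it is 35 + 100/3 = 68.3. With one dose kept at N = 210 it is 30 + 90/2 = 75, or 35 + 70/2 = 70. The low end reproduces; 80 is not reached. A dropped dose would have 30 to 35.

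**Step 1: mixing.** Let u be the probability of a UC-worsening AE and o that of any other AE, assumed independent. Then any-AE = 1 − (1 − u)(1 − o). All rates are assumptions. With o = 40% on placebo:

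| u placebo / drug | any-AE placebo | any-AE drug if o is also 40% | apparent difference | excess in o on drug that gives equal any-AE |
|---|---|---|---|---|
| 10% / 5% | 46% | 43% | −3.0 | +3.2 |
| 15% / 5% | 49% | 43% | −6.0 | +6.3 |
| 20% / 10% | 52% | 46% | −6.0 | +6.7 |
| 25% / 10% | 55% | 46% | −9.0 | +10.0 |
| 15% / 15% | 49% | 49% | 0 | 0 |

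The last column solves 1 − (1 − any)/(1 − u_drug) − o. For the second row: 1 − 0.51/0.95 = 46.3%, against 40%. Letting o on placebo run from 30% to 50% over the unequal flare pairs, the concealed excess is 2.6 to 11.7 points.

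With a true non-UC excess of 5 points (45% placebo, 50% drug), the endpoint shows:

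- flares 10% / 5%: 50.5% v 52.5%, +2 points
- flares 15% / 7.5%: 53.25% v 53.75%, +0.5 points
- flares 20% / 10%: 56% v 55%, −1 point

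**Step 2: can preferred-term tables recover the non-UC proportion?** SAP 4.8.1 counts a subject once per term, and one subject may appear under several terms. The proportion with at least one non-UC AE therefore lies somewhere between the largest non-UC row and the sum of those rows. Subtracting the UC row from the any-AE row fails too. In the 15% / 5% case with o = 40% in both arms, subtraction gives 49 − 15 = 34% on placebo and 43 − 5 = 38% on drug, a spurious 4-point excess, because subjects with both kinds of event are removed. Subject-level data are needed.

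**Step 3: precision.** The 95% half-width for a difference is 1.96 × √(p₀q₀/n₀ + p₁q₁/n₁). At p = 50%:

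- 70 per arm: 1.96 × √(2 × 0.25/70) = 16.6 points
- 80 per arm: 15.5 points
- dropped dose of 30 to 35 against 70 on placebo: about 21 to 20 points

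**The case against.** The strongest reply is that the plan already separates UC events. Protocol 7.5, SAP 4.8.1 and the SAP 7.1 table list provide treatment-emergent events by system organ class and preferred term, by severity and by relationship, plus SAEs and events of special interest. A monitoring committee that may be unblinded reviews safety about quarterly. A term for UC worsening would have its own row per arm, so serious toxicity is unlikely to disappear. This stands: only the headline proportions are affected. It does not supply the missing quantity, as Step 2 shows. The relationship table is a weak substitute, because Appendix F uses not, unlikely, possibly and related, whereas SAP 4.8.1 counts definite, probable and possible.

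It is also fair that the Appendix F definition is generic, and that neither document says in words that a flare is recorded as an AE. A reader might infer that the plan deliberately counts every flare; the documents support only that nothing excludes it.

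The assumed shifts are small beside a ±16.6-point interval, and a reader could compute a difference and interval from the printed counts. Both are true. They make the second gap a matter of reporting rather than lost information.

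Finally, PTG-100 acts in the gut, so removing terms for UC worsening could also remove gut events the drug causes. This stands and limits how the extra row may be used.

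**Conclusion.** The concern holds in a limited form. UC worsening is inside the any-AE and SAE proportions by definition, and these could favour an effective dose. That requires flares to be recorded as AEs and to be less frequent on drug. Under the assumed rates the concealed excess is 2.6 to 11.7 points; it is zero with equal flare rates. The sizes rest wholly on assumed rates and on independence of the two kinds of event.

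Two stronger readings should be resisted. A reader might infer that an effective dose will look safer than it is; the documents give no rates from which to say so, and the detailed tables would show UC events. A reader might also take the missing interval as the cause of the masking. It is not: an interval on the same endpoint would show imprecision and leave the offset untouched. The absence of a difference and interval is a separate gap that remains even if flare rates are equal.

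This is a cheap improvement to the reporting of a primary endpoint. It does not invalidate the safety analysis.

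**What to change.** In SAP 4.8.1, keep the all-event treatment-emergent and SAE proportions exactly as defined. Beside each, add a supplementary row that excludes preferred terms describing worsening of UC. Fix the term list before unblinding, and have it written by people without access to the interim results. Protocol 2.1 describes UC by bloody diarrhoea, cramps and fatigue, so the list must say whether such symptom terms are included. For each version report the dose-minus-placebo difference with a 95% interval, labelled descriptive. A footnote saying whether sites were to record UC worsening as an AE would help in reading both rows.

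The cost is a short term list and a few table rows, with no new data. The downside is that the exclusion may remove some drug-caused gut events, so the excluded version must be read beside the all-event version and must not replace it.

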2.1 Background and Rationale

Protagonist Therapeutics, Inc. is developing PTG-100 as a potential oral therapy for patients with moderate to severe active ulcerative colitis (UC). PTG-100, a peptide dimer comprised of natural and unnatural amino acids and a homologated amide bond, is an orally-stable peptide that binds specifically to $\alpha 4\beta 7$ integrin on leukocytes.

PTG-100 is designed to be stable against various forms of gastrointestinal (GI) degradation and to target $\alpha 4\beta 7$ integrin within the GI tissue compartment. Animal pharmacokinetic (PK) studies have shown these peptides are orally stable because they can be detected as full-length intact peptides in gut tissues and faeces after oral dosing. The PK studies have also shown the oral peptides have high exposure in the colon, small intestine, and to a lesser extent in the mesenteric lymph nodes with less than 0.5% systemic bioavailability; therefore, its presence is largely restricted to the GI tract.

PTG-100 binds specifically to $\alpha 4\beta 7$ integrin on leukocytes, the same target as the approved antibody therapeutic vedolizumab (Entyvio[®]). PTG-100 is a potent and selective inhibitor of $\alpha 4\beta 7$ integrin with binding selectivity identical to the antibody product vedolizumab. PTG-100 does not bind to $\alpha 4\beta 1$ integrin. The $\alpha 4\beta 7$ integrin, which is primarily involved in the recruitment of leukocytes to the GI tract, is present on the cell surface of a small population of circulating T- and B-lymphocytes. The major ligand for $\alpha 4\beta 7$, mucosal addressin cell adhesion molecule 1 (MAdCAM-1), is selectively expressed on the endothelium of the intestinal vasculature and is present in increased concentrations in inflamed tissue. Through blockade of leukocyte trafficking in the gut, PTG-100 may inhibit inflammation in the GI tract, potentially reducing the signs and symptoms of active UC.

Vedolizumab (Entyvio[®]), an intravenously administered monoclonal antibody that similarly targets $\alpha 4\beta 7$ integrin, has been approved for the treatment of adult patients with moderate to severe active UC who have had an inadequate response with, lost response to, or were intolerant to a tumour necrosis factor-alpha (TNF- α) blocker or immunomodulator; or had an inadequate response with, were intolerant to, or

^a Information supplied by the Sponsor.

demonstrated dependence on corticosteroids.¹ Vedolizumab has also been approved for treatment of patients with Crohn's disease (CD).² Therefore, it is considered that blockade of this interaction is a safe and effective therapy for inflammatory bowel disease.

Ulcerative colitis is a chronic inflammatory bowel disease characterised by bloody diarrhoea, abdominal cramps, and fatigue.³ Current medical therapy has important limitations. Aminosalicylates are only modestly effective; glucocorticoids can cause unacceptable adverse events (AEs) and do not provide a benefit as maintenance therapy.⁴⁻⁶ Tumour necrosis factor-alpha antagonist antibody drugs, although efficacious, may predispose patients to serious infection, a risk of malignancy, and development of anti-drug antibodies (ADA).⁷⁻⁹ Vedolizumab (Entyvio[®]) is administered as an intravenous (IV) infusion with potential for systemic infection and risk of immunogenicity.^{1,2,10} Therefore, new treatment strategies are needed for patients with UC.

Due to the inconvenience of injectable therapies, associated safety risks of systemic treatment, and risk of development of ADA, PTG-100, an orally-stable, GI-restricted peptide therapeutic candidate that targets $\alpha 4\beta 7$, may provide a significant benefit to patients with moderate to severe UC.

Both in vitro and in vivo pharmacology studies have been conducted to assess the activity, mechanism of action, and toxicity of PTG-100. PTG-100 is a potent and selective inhibitor of $\alpha 4\beta 7$ with binding properties highly similar to the antibody product vedolizumab. Similar to vedolizumab, PTG-100 does not bind $\alpha 4\beta 1$ integrin. A dextran sulphate sodium-induced colitis mouse model demonstrated that PTG-100 administration induced a dose-dependent reduction in $\alpha 4\beta 7+$ memory T cell homing to inflamed gut tissue and a significant improvement in mucosal damage as assessed by blinded endoscopy. Pharmacokinetic studies show that drug levels are much higher in GI tissues compared to blood, which suggests that drug exposure in the GI tissues is the principal driver for the in vivo pharmacology. Fluorescence-activated cell sorter (FACS) analysis of whole blood from healthy cynomolgus monkeys demonstrated that a peripheral blood receptor occupancy (RO) of less than 50% is correlated with in vivo efficacy in the mouse studies. Levels of circulating $\alpha 4\beta 7+$ memory T cells were increased when normalised to total CD4 cells following PTG-100 dosing, confirming that blocking homing of $\alpha 4\beta 7+$ memory T cells redistributes these cells to the blood.

In 42- and 90-day (Good Laboratory Practice [GLP]) toxicology studies, no adverse toxicological findings were observed at once daily (QD) doses up to 90 mg/kg/day and 75 mg/kg/day in rats and monkeys, respectively. The no observed effect level (NOEL) in rats was 90 mg/kg/day, the highest level evaluated. In the monkey study, the no observed adverse effect level (NOAEL) was considered to be 75 mg/kg/day, the highest dose tested. Also, histology from the 90-day toxicology studies demonstrated no adverse testicular findings.

Reproductive and developmental toxicity studies of limited scope (6 dams/group) in rats and rabbits have been completed. There were no maternal or developmental effects noted in either study. The maternal and developmental NOEL for PTG-100 was 90 mg/kg/day in pregnant rats and 75 mg/kg/day in pregnant rabbits, the highest dose levels tested in these studies. Definitive reproductive and developmental toxicity studies to evaluate embryo-foetal development will be completed prior to the Phase 3 clinical program.

PTG-100 did not inhibit the human Ether-à-go-go Related Gene potassium channel current. No effects of PTG-100 were observed on the cardiovascular or respiratory systems in conscious monkeys, or in central nervous system functional assessment (Irwin) or GI motility studies in rats. In vitro GLP genotoxicity tests were negative, indicating a low genotoxic potential.

Protagonist has completed a Phase 1 randomised, double-blind, placebo-controlled, 3-part study (Study PTG-100-01) of PTG-100 in 78 normal healthy male volunteers in Australia. Sixty-four of the 78 subjects were treated with PTG-100. Parts 1 and 2 evaluated single and multiple ascending doses of PTG-100, respectively, up to a maximum daily dose of 1000 mg using a liquid phosphate buffer (PB) formulation of PTG-100. Doses up to 1000 mg/day were tested as a single dose and as QD dosing for 14 days. Part 3 was a single dose cross-over study of PTG-100 capsule formulation compared to solution-based PB formulation. These data informed the selection of doses in Phase 2 ([Section 2.2](#)).

In this Phase 1 study, PTG-100 was well tolerated; there were no serious AEs (SAEs) or dose-limiting toxicities observed. All AEs were mild to moderate in severity. No dose-dependent increase in AEs was noted. There were no clinically significant abnormalities or trends in clinical labs, electrocardiograms (ECGs), or vital signs. The maximum dose tested for both single and multiple dosing was 1000 mg; no dose-limiting toxicities were observed at this or any doses.

Consistent with the preclinical data in mice, rats, and cynomolgus monkeys, in Study PTG-100-01, the plasma exposure to PTG-100 was extremely low (< 1%) as determined by the area under the concentration-time curve (AUC) and maximum observed concentration (C_{max}), thus reflecting the GI-restricted nature of the drug. In a small cohort of subjects administered a single dose of PTG-100 (300 mg), the systemic exposure (as measured by C_{max} and AUC from time 0 to the time of the last sample collection [AUC_{0-t}]) of PTG-100 when given to participants after a high-fat meal was approximately 30% of that for PTG-100 administered under fasted conditions. All subjects in the multiple ascending dose (MAD) cohorts in the trial were fed a standard diet. There was minimal drug accumulation at Day 14 in the MAD cohorts, related to the relatively short half-life in the blood.

Dose-dependent increases in blood RO and reduction in receptor expression (RE; eg, receptor down-regulation), as reflecting target engagement in the GI tissue compartment, were observed, thus supporting evidence of sustained target engagement and pharmacologic activity of PTG-100 in healthy volunteers comparable to the data in mouse and cynomolgus monkey studies. Saturating levels of receptor down-regulation were observed at the 300-mg dose level following multiple dose exposure. Blood RO and RE levels in the healthy volunteers (at the 300-mg dose level) exceeded threshold levels in the healthy mice at comparable dose levels (based on allometric scaling; eg, approximately 50 mg/kg/day); this dose threshold also correlated with inhibition of lymphocyte trafficking and improvements in disease activity in the colitis mouse studies. Therefore, the data suggest a potentially efficacious dose of 300 mg in patients with UC.

To support the use of the capsule formulation in Study PTG-100-02, in vivo PK bridging studies in cynomolgus monkey and normal healthy volunteers have demonstrated that the relative bioavailability of the capsule formulation compared to the liquid PB formulation (used in the GLP toxicology studies and Phase 1 single ascending dose and MAD cohorts) was approximately 60% based on AUC_{0-t} and AUC from time 0 to infinity. Despite the lower plasma exposure of the capsule formulation compared to the liquid formulation, the pharmacodynamic (PD) effects (eg, blood RO and RE) were highly similar between the capsule and liquid formulations. These data support the use of the capsule formulation in the Phase 2b clinical trial at doses established by single and multiple dose cohorts using the liquid PB formulation.

Further information about the preclinical and Phase 1 studies are provided in the Investigator's Brochure (IB).

